6.4.2. Additional consideration

1. The analysis will also be performed on subjects having confirmed HZ episode from Zoster-006/022.
2. Listing for all the suspected HZ episodes will be presented.

7. ANALYSIS INTERPRETATION

All analyses are descriptive.

8. CONDUCT OF ANALYSES**8.1. Sequence of analyses**

Description	Analysis ID	Disclosure Purpose (CTRS=public posting, SR=study report, internal)	Dry run review needed (Y/N)	Study Headline Summary (SHS) requiring expedited communication to upper management (Yes/No)	Reference for TFL
End of study	E1_01	Study report	Y	Yes	Section 13 of the SAP and TOC dated 26-FEB-19

8.2. Statistical considerations for interim analyses

All analyses will be conducted on final data and therefore no statistical adjustment for interim analyses is required.

9. CHANGES FROM PLANNED ANALYSES

Following are the changes from the planned analysis:-

1. As per protocol, it was mentioned that ‘all analyses may be performed by age group at vaccination in the ZOSTER-006/022 (50-59, 60-69 and ≥ 70 YOA). However, team felt it is more reasonable to present the analysis based on age (by Year of birth) at first vaccination in current study. As the ≥ 80 YOA population in current study has increased in number because the cohort has aged, so the sub-group considered for the analysis has also been modified by dividing ≥ 70 YOA sub-group, further, into two (70-79 and ≥ 80 YOA) looking at the frequency of the subjects in these age groups (70-79 YOA = 3349 and ≥ 80 YOA = 2109). The age sub-group to be considered now will be (50-59, 60-69, 70-79 and ≥ 80 YOA)’ based on the age (by Year of birth) at first vaccination in current study.
2. Table on presentation of fatal SAE has been added under additional consideration for safety analysis based on CBER feedback following Shingrix After Action Review (AAR) post Type C meeting with CBER.

3. Safety analysis by previous confirmed HZ episode (HZ episodes from Zoster-006/022 study) has been added.
4. Suspected HZ episodes in this study will also be presented on confirmed previous HZ episodes from Zoster-006/022 study.

10. LIST OF FINAL REPORT TABLES, LISTINGS AND FIGURES

The TFL TOC provides the list of tables/listings and figures needed for the study report. It also identifies the tables eligible for the analysis and their role (synopsis, in-text, post-text, SHS, web disclosure). Note that all TFL aimed to be included as post-text are noted as post-text even if these are tabulation of individual data such as listing of SAE. The post-text material contains all source material for the study report and accordingly a post-text table may be redundant with an in-text table.

The following group name will be used in the TFLs:

Group order in tables	Group label in tables	Group definition for footnote	Pooled Groups label in tables	Pooled definition for footnote
1	HZ/su	Herpes Zoster subunit vaccine	NA	NA

NA=Not applicable

The following sub-group names will be used in the TFLs:

Sub-group order in tables	Sub-group label in tables	Sub-group definition for footnote
1	50-59YOA	Subjects aged 50-59 years*
2	60-69YOA	Subjects aged 60-69 years*
3	70-79YOA	Subjects aged 70-79 years
4	≥80YOA	Subjects aged 80 years and over *

*age at first vaccination in Zoster-056 study

11. ANNEX 1 STANDARD DATA DERIVATION RULES AND STATISTICAL METHODS

11.1. Statistical Method References

The exact two-sided 95% CIs for a proportion within a group will be the Clopper-Pearson exact CI [Clopper CJ, Pearson ES. The use of confidence or fiducial limits illustrated in the case of binomial. *Biometrika*. 1934;26:404-413].

11.2. Standard data derivation

11.2.1. Date derivation

- SAS date derived from a character date: In case day is missing, 15 is used. In case day and month are missing, 30 June is used.
- Onset day for an event (AE, medication, vaccination, ...): The onset day is the number of days between the last study vaccination and the onset/start date of the event. This is 0 for an event starting on the same day as a vaccination. See SAS date derived in case the start date of the event is incomplete.
- Duration: Duration of an event is expressed in days. It is the number of days between the start and the stop dates + 1. Therefore duration is 1 day for an event starting and ending on the same day.

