³ Only applicable for females of childbearing potential. A urine pregnancy test is sufficient. A serum pregnancy test instead of a urine pregnancy test should only be considered if required by country, local or ethics committee regulations.

⁴ One diary card for unsolicited AEs up to 30 days post vaccination

⁵ Subject will be instructed to contact their study site immediately if he/she manifests any symptoms he/she perceives as serious and, in case of pregnancy for women of childbearing potential

⁶ Subjects will be asked to mail the diary cards 30 days after Visit 2 if their Month 3 contact will be by phone or to bring along their diary card if their Month 3 contact will be a site visit. Operational details will be defined in the SPM

⁷ It is the responsibility of the site to follow up until the diary cards are received

Table 5 Intervals between study visits

Interval	Optimal length of interval 1	Allowed interval
Visit 1→Visit 2	60 days (2 months)	49 days - 83 days
Visit 2 → Visit 3/Month 3 Phone contact	30 days (1 month)	30 - 48 days
Visit 2 → Month 8 Phone contact	180 days (6 months)	180 - 240 days
Visit 2 → Month 14* Phone contact	365 days (12 months)	335 –395 days

¹ Whenever possible the investigator should arrange study visits within this interval

*i.e. 12 months post dose 2

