8.3. Detecting and recording adverse events, serious adverse events and pregnancies

8.3.1. Time period for detecting and recording adverse events, serious adverse events and pregnancies

All AEs starting 30 days following administration of each dose of study vaccine (Day 0 to Day 29) must be recorded into the appropriate section of the eCRF, irrespective of intensity or whether or not they are considered vaccination-related.

The time period for collecting and recording SAEs will begin at the first receipt of study vaccine and will end 12 months following administration of the last dose of study vaccine for each subject. See Section 8.4 for instructions on reporting of SAEs.

The occurrence of suspected HZ will constitute an AE or SAE, as appropriate (and shall be reported in the HZ section of the eCRF [if an AE] or in the SAE and HZ section of the eCRF [if an SAE]). During the study, the time period for collecting and recording of suspected HZ will range from first receipt of study vaccine to study end. When a suspected HZ episode has been reported, specific clinical information about the case, following the first vaccination visit (Month 0) until study end (Month 14), will be entered into the eCRF. Please refer to the SPM for information about recording the details of suspected HZ cases.

All AEs/SAEs leading to withdrawal from the study will be collected and recorded from the time of the first receipt of study vaccine.

In addition to the above-mentioned reporting requirements and in order to fulfil international reporting obligations, SAEs that are related to study participation (i.e. protocol-mandated procedures, invasive tests, a change from existing therapy) or are related to a concurrent GSK medication/vaccine will be collected and recorded from the time the subject consents to participate in the study until she/he is discharged from the study.

The time period for collecting and recording pregnancies will begin at the first receipt of study vaccine and will end 12 Months following administration of the last dose of study vaccine. See Section 8.4 for instructions on reporting of pregnancies.

The time period for collecting and recording of pIMDs will begin at the first receipt of study vaccine and will end 12 Months following administration of the last dose of study vaccine. See Section 8.4 for instructions on reporting of pIMDs.

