6.3. Analysis of safety

6.3.1. Analysis of safety planned in the protocol

The analysis for safety will be based on the TVC.

All analysis will be performed overall and by age sub-group at vaccination in the ZOSTER-056 (50-59, 60-69, 70-79 and ≥ 80 YOA).

When appropriate, tabulations will be presented overall and by time of occurrence related to last vaccination (e.g. using windows such as Days 0-29 and more than 30 days post-vaccination).

The results for the analysis of safety will be tabulated as follows:

- The proportion of subjects with at least one report of an unsolicited AE during the 30-day (Days 0–29) follow-up period after each vaccination classified according to the MedDRA System Organ Class and Preferred Terms will be tabulated, with exact 95% CI.
- The same tabulation will be performed for grade 3 unsolicited AEs (including SAEs) and for unsolicited AEs with a relationship to vaccination. The proportion of AEs resulting in a medically attended visit will also be tabulated.
- Total number/percentages of doses (per dose and overall) followed by AEs during the 30 days (Days 0-29) follow-up period after each vaccination classified according to the MedDRA System Organ Class and Preferred Terms will be tabulated.
- SAEs will be described in detail in listing for the entire study period.
- Withdrawal due to AE(s) and SAE will be described in detail in listing for the entire study period.
- Number of subjects with pIMDs will be tabulated according to the MedDRA System Organ Class and Preferred Terms for the period during first vaccination up to 30 days post second vaccine dose, after 30 days post second vaccine dose to study end and from first vaccination to study end.

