6.3.2. Additional considerations

Following additional analyses will be performed:-

1. Number and percentage of subjects with at least one report of a grade 3 non-serious unsolicited AE during the 30-day (Days 0–29) follow-up period after each vaccination classified according to the MedDRA System Organ Class and Preferred Terms will be tabulated, with exact 95% CI.

2. Number and percentage of subjects reporting at least one SAE/ pIMD classified according to the MedDRA System Organ Class and Preferred Terms will be tabulated, with exact 95% CI with onset day of SAE during the time interval during study start to 30 days post 2nd vaccine dose, after 30 days post 2nd vaccine dose till study end and from study start till study end.
3. Number and percentage of subjects with fatal SAEs, classified by MedDRA Primary System Organ Class and Preferred Term will be presented with exact 95% CI in two ways:-
 - With onset of fatal SAE during the period starting from first vaccination to 30 days post last vaccination dose, after 30 days post last vaccination dose to study end and from first vaccination to study end
 - Who died during the period starting from first vaccination to 30 days post last vaccination dose, after 30 days post last vaccination dose to study end and entire study period.
4. Number and percentage of subjects reporting the occurrence of unsolicited adverse events classified by MedDRA Primary System Organ Class and Preferred Term within the 30-day (Days 0-29) post-vaccination period will also be presented, overall and by age sub-group with exact 95% CI on Total Vaccinated Cohort considering only subjects with a confirmed HZ episode during Zoster-006/022. The same tabulation will be performed for grade 3 unsolicited AEs and for unsolicited AEs with a relationship to vaccination.
5. Number and percentage of subjects reporting the occurrence of serious adverse event and pIMD, classified by MedDRA Primary System Organ Class and Preferred Term from first vaccination until study end will also be presented with exact 95% CI on Total Vaccinated Cohort considering only subjects with a confirmed HZ episode during Zoster-006/022.
6. List of subjects withdrawn from vaccination with reason for withdrawal will be presented from first vaccination until study end.

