11.2.2. Dose number

- The study dose number is defined in reference to the number of study visits at which vaccination occurred. More specifically dose 1 refers to all vaccines administered at the first vaccination visit while dose 2 corresponds to all vaccinations administered at the second vaccination visit even if this is the first time a product is administered to the subject.
- Associated dose: the associated dose for an event (AE, medication,...) is the most recent study dose given before an event. In case the event takes place on the day a study dose is given, the associated dose will be that of the study dose, even if the event actually took place before vaccination. For instance, if an adverse event begins on the day of the study vaccination but prior to administration of the vaccine, it will be assigned to this dose. In case a study dose is not administered and an event occurs after the subsequent study dose (e.g. 2nd study dose), the associated dose of the event will be study dose associated to the subsequent study dose (e.g. dose 2).
- The number of doses for a product is the number of times the product was administered to a subject.
- The incidence per dose is the number of visits with vaccine administered at which an event was reported among all visits with vaccine administered.

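### SAP 11.2.1 dates a day-missing event to the 15th with no bound at the dose or at the end of the collection period, so its onset day and dose can contradict what is known

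*SAP*

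**What the plan says.** SAP 11.2.1 gives one rule for a date that lacks only the day: "In case day is missing, 15 is used". The same section defines onset day: "The onset day is the number of days between the last study vaccination and the onset/start date of the event". It sends partial start dates through the imputation: "See SAS date derived in case the start date of the event is incomplete". SAP 11.2.2 then fixes the dose: "the associated dose for an event (AE, medication,...) is the most recent study dose given before an event". That section has an exception for an event on the calendar day of a vaccination, but none for an imputed date that falls on an earlier day.

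These derived values matter for two groups of tables:

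- **Unsolicited AEs.** SAP 6.3.1 tabulates "The proportion of subjects with at least one report of an unsolicited AE during the 30-day" period after each vaccination, by subject and by dose.
- **SAEs and pIMDs.** SAP 6.3.2 splits them into sub-periods, the first being those "with onset day of SAE during the time interval during study start to 30 days post 2nd vaccine dose".

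The protocol says what is known about a recorded AE whatever its date. Section 8.3.1: "All AEs starting 30 days following administration of each dose of study vaccine (Day 0 to Day 29) must be recorded". Table 4, footnote 4, provides: "One diary card for unsolicited AEs up to 30 days post vaccination". Section 5.6.14 has cards handed out at each vaccination visit. Collection of SAEs and pIMDs starts at the first dose and ends 12 months after the last.

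**The concern.** A non-serious AE is recorded because it began in the 30 days from a given dose. The imputation ignores this and can produce a date that contradicts it at either end.

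- **Dated before Dose 1.** With Dose 1 on 20 March and an AE recorded only as March, the derived onset is 15 March. No study vaccine precedes it, so neither onset day nor associated dose is defined, and the SAP does not say how the event is handled.
- **Dated before Dose 2.** If 20 March is Dose 2, the AE attaches to Dose 1, well after that dose's Day 29.
- **Dated after Day 29.** With a dose on 10 March and an AE recorded only as April, the derived onset is 15 April, Day 36, although the AE was collected for Days 0–29.

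Unsolicited AEs in Days 0–29 are a primary endpoint, and the per-dose tables need the associated dose. AEs that cluster soon after vaccination are dated before the dose more often. Only events with a known month and a missing day are considered here.

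**Working it through.** The plan gives no misdating rate to reproduce, so the rule was applied to every combination of dose date and true onset.

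**Inputs from the documents:** imputed day 15 and the onset-day definition (SAP 11.2.1); dose rule (SAP 11.2.2); AE window Days 0–29 (protocol 8.3.1, SAP 6.3.1); interval between doses 49 to 83 days (protocol Table 5); about 12 months of follow-up after Dose 2, taken as 365 days.

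**Assumptions, not in the documents:** dose dates uniform over a calendar year; true onset uniform over Days 0–29, with other patterns as sensitivity; the share of AEs that lack the day.

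**Formula.** Let D be the dose date and k the true onset day. The derived onset day is x = (15th of the month containing D + k) − D. The event is dated before the dose if x < 0 and after the window if x > 29.

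**Hand check, 30-day months.** There are 30 × 30 = 900 pairs of dose day d and onset day k.

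- Before the dose: d is 16 or later and onset is in the same month, which gives 31 − d values of k. The sum over d = 16 to 30 is 15 + 14 + … + 1 = 120, and 120/900 = 13.3%.
- After Day 29: d is 15 or earlier and onset is in the next month, so x = 45 − d ≥ 30, which gives d − 1 values of k. The sum over d = 1 to 15 is 0 + 1 + … + 14 = 105, and 105/900 = 11.7%.
- Total 225/900 = 25.0%.

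**Real calendar.** Over 365 × 30 = 10,950 pairs, 13.9% fall before the dose and 11.5% after Day 29, 25.4% in all. A floor at the dose date alone would leave the 11.5%.

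**Other onset patterns:**

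| True onset | Dated outside Days 0–29 |
|---|---|
| Uniform, Days 0–29 | 25.4% |
| Uniform, Days 0–6 | 40.8%, all before the dose |
| Exponential, scale 3 days | 42.5% |
| Exponential, scale 7 days | 33.7% |
| Centred on Day 14.5, SD 3 days | 8.9% |
| All on Day 15 | 1.9% |

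**Dose 2 events dated before Dose 2.** The imputed date is 1 to 16 days before Dose 2. The event therefore lands on Day 33–48 after Dose 1 at a 49-day interval (49 − 16 to 49 − 1), Day 44–59 at 60 days and Day 67–82 at 83 days. None falls in the Days 0–29 window of Dose 1. In the 20 March example with a 49-day interval it is Day 49 − 5 = 44.

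**Share of all Days 0–29 AEs, uniform onset.** This is the missing-day share × 0.254: 1% gives 0.25%, 2% gives 0.5%, 5% gives 1.3%. It stays below 1% unless more than 1%/0.254 = 3.9% of AEs lack the day.

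**SAEs and pIMDs with the day missing**, onset uniform from Dose 1 to 365 days after Dose 2:

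| Dose interval (days) | Before Dose 1 | Wrong or no period |
|---|---|---|
| 49 | 1.01% | 3.67% |
| 60 | 0.98% | 3.58% |
| 83 | 0.93% | 3.40% |

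The last column counts onsets dated after the end of follow-up. Leaving those out gives 2.6–2.8%.

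**The case against.** The strongest reply is that the rule may hardly ever operate. It sits in an annex of standard derivations that also covers medications and vaccinations. Nothing shows that the eCRF accepts an AE onset without a day, and the sponsor's data-management standards and the Study Procedures Manual are not available to check. Cards are verified with the subject (protocol 5.6.14), analyses run on cleaned data (10.10.1), and the analysis plan can be reassessed after significant non-compliance in event reporting (10.5). All analyses are descriptive and single-arm, so no test or comparison is affected. A subject with another correctly dated AE still counts in the row for at least one symptom. This stands, and it limits the severity. It does not supply the missing rule: the SAP keeps an imputation because it expects some partial dates, and a few missing days would not amount to significant non-compliance.

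A second reply is that misdated AEs need not be dropped. Non-serious AEs are collected for Days 0–29 in the first place, and SAP 11.2.2 counts incidence per dose by vaccination visits at which an event was reported. This also stands. A reader might infer that a quarter of day-missing AEs are lost from the primary tables, but no text says that the derived onset day filters AEs already collected for the window. Selection by onset day is an inference; the SAP states no other rule.

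A reader might also put the whole 25.4% down to the missing bound at the dose date. Only 13.9 points come from there; the other 11.5 come from the absence of a cap at Day 29.

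**Conclusion.** The gap is real and minor; confidence is medium. SAP 11.2.1 and 11.2.2 can give a day-missing event an onset day and dose that contradict the period for which it was recorded, and before Dose 1 they give none.

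For non-serious AEs, 25.4% is an illustration that rests on uniform dose dates and uniform onset. The range of 1.9% to 42.5% shows how far it depends on the onset pattern, on which the documents are silent. It applies only to AEs with a known month and no day. Their number is not given, so the effect on the primary proportions cannot be sized; the 0.25–1.3% rests on assumed shares. What is shown is that events are dated outside the window, not that they are lost from a table. For SAEs and pIMDs, the 3.4–3.7% likewise applies only to those with the day missing and assumes uniform onset.

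**What to change.** In SAP 11.2.1 keep the 15th for a missing day and add bounds:

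- **Non-serious AEs recorded for the Days 0–29 period of a dose, from a diary card or from questioning** (other than pIMDs, suspected HZ and AEs leading to withdrawal). If the known month overlaps that period and the record does not show onset outside it, set the imputed date no earlier than that dose and no later than its Day 29, and associate the AE with that dose.
- **SAEs, pIMDs, suspected HZ and AEs leading to withdrawal.** Set the imputed date no earlier than Dose 1, unless the record shows earlier onset, and no later than the subject's last contact.
- **Listings.** Flag every imputed onset.

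For non-serious AEs truly from Days 0–29 this leaves none dated outside the window under any pattern tried, and the bounded date stays in the recorded month. With uniform onset the mean absolute dating error falls from 7.6 to 6.2 days. For SAEs and pIMDs, a floor at Dose 1 alone leaves 2.5–2.7% in a wrong or no period. With the upper bound as well (last contact at 365 days) it is 1.7–1.8%, all in the wrong sub-period.

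The cost is a few lines of SAP text, the derivation program and a flag column. It also needs the database to keep the link between an AE and the dose period for which it was recorded; the documents describe transcription of the cards but do not show that this link is kept.

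There are two downsides. Imputed onsets pile up at the bounds: 15.7% on Day 0 and 13.2% on Day 29 with uniform onset, and 44% on Day 0 if onset is in Days 0–6. Day-missing events that truly began in Days 30–59 but were recorded for the window are also counted in it more often, 49% against 14% now. The protocol asks only for Days 0–29 events, so these should be few.

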11.2.2. Dose number

- The study dose number is defined in reference to the number of study visits at which vaccination occurred. More specifically dose 1 refers to all vaccines administered at the first vaccination visit while dose 2 corresponds to all vaccinations administered at the second vaccination visit even if this is the first time a product is administered to the subject.
- Associated dose: the associated dose for an event (AE, medication,...) is the most recent study dose given before an event. In case the event takes place on the day a study dose is given, the associated dose will be that of the study dose, even if the event actually took place before vaccination. For instance, if an adverse event begins on the day of the study vaccination but prior to administration of the vaccine, it will be assigned to this dose. In case a study dose is not administered and an event occurs after the subsequent study dose (e.g. 2nd study dose), the associated dose of the event will be study dose associated to the subsequent study dose (e.g. dose 2).
- The number of doses for a product is the number of times the product was administered to a subject.
- The incidence per dose is the number of visits with vaccine administered at which an event was reported among all visits with vaccine administered.

